3.4.3 Exploratory Efficacy Endpoints

Baseline pharmacogenomics (genetic/ribonucleic acid [RNA] testing) will be evaluated. Evaluation of biomarkers at Baseline, the Transition Visit, and Week 16, and change from Baseline to Transition and Transition to Week 16 will be performed.

The exploratory efficacy endpoints will be prespecified in this document but performed at a later time by the study sponsor.

3.4.4 Subgroup Analysis

The primary efficacy endpoint may be summarized for the Per-Protocol and Completer Population within subgroups defined by age (Median value of IIT Population), gender, background PAH therapy at Baseline (1. none, 2. Endothelin Receptor Antagonist [ERA] alone, 3. Phosphodiesterase-5 [PDE-5] inhibitor/sGC stimulator alone, or 4. ERA + PDE-5 inhibitor/sGC stimulator), or baseline disease severity (as defined by 6MWD categories, WHO functional classification for PAH, REVEAL 2.0 risk score, time since PAH diagnosis).

3.5 Pharmacokinetic Assessment

No pharmacokinetic assessment is performed in this study.

3.6 Pharmacodynamic Assessment

No pharmacodynamic assessment is performed in this study.

3.7 Safety Assessment

Safety data will be summarized based on the Safety Population.

3.7.1 Adverse Events (AEs) and Prostanoid AEs

Adverse events will be captured from when the subject signs the informed consent form (ICF) until the subject completes the study or is withdrawn from the study. All AEs will be coded to system organ class and preferred term using MedDRA version v 21.0. Treatment-emergent adverse events (TEAEs) are defined as AEs that start after the first dose of Remodulin.

Adverse events related to study drug will be those with a causality of possibly or probably related.

The severity of a given AE is the maximum of all severities recorded during initial recording and all reassessments of the AE.

An overview of AEs will be provided including counts and percentages of subjects and event counts (an AE record regardless of reassessment, only contributes once into the event count) with the following:

- Any TEAEs (overall and by maximum severity)
- Any serious AEs (SAEs)
- Any treatment-emergent serious AEs (TESAEs)
- Any TEAEs leading to discontinuation of study
- Any TEAEs leading to discontinuation of Remodulin
- Any TEAEs leading to discontinuation of Orenitram
- Any SAEs leading to death

Counts and percentages of subjects and event counts will also be presented by system organ class and preferred term for each of the categories in the overview, except SAEs, if there are at least 5 adverse events in the categories.

Figures for visualizing the number of days an AE falls into each AE severity category (Mild, Moderate, Severe) and changes in AE severity over time may be provided by sponsor.

For each of the "Prostanoid AEs" defined by section 3.3.1.9 of the protocol (headache, diarrhea, nausea, flushing, jaw pain, extremity pain, and vomiting):

- The counts and percentages of patients and event counts who report the Prostanoid AE will be summarized, as well as a breakdown of the maximum severity reported (e.g. mild, moderate, severe).
- This will be reported separately for each treatment phase.
- AEs that occur in more than one treatment phase (e.g. a 'severe' headache that began
 in the Remodulin phase that continued as a 'severe' or 'mild' to the Transition phase will
 be counted in both treatment phases, with corresponding severities based on the
 maximum severity in each phase) will be counted in each treatment phase.
- Changes in severity of Prostanoid AEs over the entire study period may be listed, summarized, and/or depicted graphically for each patient. This may be performed by the study sponsor.
- The number of days which the AE was reported and the corresponding severity may be summarized for each treatment phase (i.e. Remodulin phase, Transition phase, Orenitram phase). For these summaries, the AE Reassessment date will be used as the start and end dates for an AE which changes in severity, and the AE End Date will be the end date for the AE. This may be performed by the study sponsor.

Example:

Headache occurring in Remodulin phase

AE Start Date: 1/10/2022 severity: mild

AE Reassessment Date 1: 1/22/2022 severity: moderate
AE Reassessment Date 2: 2/01/2022 severity: moderate

AE End Date: 2/05/2022

Mild: 12 days (1/10/2022 to 1/22/2022)

Moderate: 14 days (1/22/2022 to 2/5/2022)

Severe: 0 days

A by subject listing will be provided for all of the AEs and listings will also be presented specifically for SAEs and TEAEs leading to discontinuation of study drug.

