^a Screening and Baseline assessments can be conducted up to 28 and 14 days prior to starting the Remodulin infusion, respectively. Screening must occur prior to Baseline assessments to confirm eligibility. Subjects with short-term musculoskeletal conditions (eg, sprained ankle) can be re-screened so that assessments aren't impacted by unusual or extenuating circumstances (refer to Section 7.1.1).

- b Following completion of Baseline assessments, subjects will be initiated on Remodulin at 2 ng/kg/min SC or IV in an inpatient or outpatient setting. IV Remodulin may be administered through an indwelling central venous catheter or a peripherally inserted catheter, as clinically indicated. For subjects receiving IV Remodulin through a central venous catheter, it is recommended that the central venous catheter be retained for at least 28 days after the transition from Remodulin.
- ^c The assessments of Week 16/Early Study Withdrawal Visit can occur over 5 days so that assessments can take place on separate days if needed. All assessments should be conducted prior to withdrawing from the study, prior to discontinuation of Orenitram or Remodulin, and as close as possible to the last dose taken by the subject.
- d The subject's PAH diagnosis date, past (noncurrent) PAH medications, PAH etiology, and WHO FC will be recorded.
- ^e These patient-reported outcomes should be completed by subjects prior to other assessments and before imparting news regarding status of their disease. Subjects should be allowed to complete the questionnaires at their own pace, and with minimal help from others.
- f Optional: RHC does not need to be conducted if the patient has an RHC within 180 days of Baseline with a cardiac index ≥2.0 L/min/m² with no changes in PAH medication regimen since the RHC. If an RHC is performed at Screening, values should be obtained for mean right atrial pressure (mRAP) and pulmonary vascular resistance (PVR) to calculate the Screening REVEAL 2.0 risk score.
- g The subject's prior PAH medications and concomitant medications should be recorded on the eCRF.
- h The Investigator will record the subject's concomitant medications and record whether the concomitant medication was used to treat an adverse event (including whether prostanoid adverse event or not). For this study, prostanoid adverse events include headache, diarrhea, flushing, nausea, jaw pain, extremity pain, and vomiting.

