9.1.1 Adverse Event

An AE is any untoward medical occurrence in a subject occurring to a subject during a clinical study whether or not it is related to the study drug. An AE may include an intercurrent illness, injury, or any other concomitant impairment of the subject's health, as well as abnormal laboratory findings if deemed to have clinical significance. Adverse events may also include worsening of an existing symptom or condition or post-treatment events that occur as a result of protocol-mandated procedures.

Events related to prostanoid therapy captured by the AE Bothersome Survey (Appendix E) should only be recorded as an AE and should only be captured as an SAE if the event is unusual with respect to intensity, frequency, or duration as compared with symptoms in the subject's medical history.

Events attributable to the progression of the disease under study (listed in Table 9-1) and events attributable to PAH symptomatology captured by PAH Symptom Score (Section 3.3.1.2) should be recorded as an AE or captured as an SAE if the event is unusual with respect to intensity, frequency, or duration as compared with symptoms in the subject's medical history, or if there is a reasonable possibility that the event was caused by the study drug.

Anorexia Palpitations

Abdominal pain Peripheral edema/generalized edema

Dizziness Presyncope

Dyspnea/dyspnea on exertion Pulmonary hypertension, exacerbation of

Exercise tolerance decreased Right heart failure/right ventricular failure

Syncope

Weight loss

Weight gain

Table 9-1 Adverse Events Attributable to the Progression of Disease

Note: Symptoms of right ventricular failure/right heart failure can include, but are not limited to, ascites, cyanosis, tachycardia, and other cardiac arrhythmias. The effects of pulmonary hypertpension and right ventricular failure/right heart failure can include cardiac arrest and death.

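### TEAEs are defined by start date alone, so an AE that begins between consent and first dose, worsens on drug and stays in one record is left out of the treatment-emergent tables

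*SAP*

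**What the plan says.** SAP section 3.7.1 sets the collection window: "Adverse events will be captured from when the subject signs the informed consent form (ICF) until the subject completes the study or is withdrawn". The window opens well before treatment. Under the Protocol's schedule of events (section 3.2), "Screening and Baseline assessments can be conducted up to 28 and 14 days prior to starting the Remodulin infusion, respectively".

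The treatment-emergent flag in the same SAP section depends only on onset: "Treatment-emergent adverse events (TEAEs) are defined as AEs that start after the first dose of Remodulin". Neither document extends it to AEs that are already present and then worsen.

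SAP section 3.7.1 also describes how a record with changing severity is handled. For counting, "an AE record regardless of reassessment, only contributes once into the event count". For grading, "The severity of a given AE is the maximum of all severities recorded during initial recording and all reassessments of the AE". Reassessment dates are used for the summaries of days at each severity, which are optional: "For these summaries, the AE Reassessment date will be used as the start and end dates for an AE which changes in severity". They play no part in the TEAE flag.

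Protocol section 9.1.1 adds: "Adverse events may also include worsening of an existing symptom or condition". It does not say whether worsening of an AE already on the eCRF should be opened as a new record.

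**The concern.** Treatment-emergent tables are meant to show what appeared or got worse on drug. A rule based on start date alone captures the first and misses the second whenever the worsening stays inside a record opened before dosing.

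Two features of this plan make that matter more than usual. SAP section 3.7.2 drops summaries and listings of vital signs and laboratory tests, so AE output carries most of the safety evidence. And the interim analysis in SAP section 4.1 has safety as its stated purpose, yet the AE overview is the only AE output it lists. Most rows of that overview depend on the TEAE flag. The by-phase prostanoid tables, the AE Bothersome Survey and the AE listings are not on the interim list.

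Tolerability is also part of the study hypothesis (Protocol section 1.4), and discontinuation because of AEs is part of its rationale (section 1.3). The rows for TEAEs leading to discontinuation bear directly on both.

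**Working it through.** **1. Confirm the record structure.** The SAP's worked headache example has one start date (1/10/2022), two reassessment dates and one end date (2/05/2022). By subtraction, 1/22 − 1/10 = 12 days mild and 2/05 − 1/22 = 14 days moderate, which matches the SAP. The example shows a severity change held inside one record whose start date does not move.

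**2. Apply the flag to four illustrative records.** Assume a first Remodulin dose on 15 January 2022. The SAP rule is: TEAE if start date > first-dose date. The amended rule adds: or a post-dose severity above the pre-dose severity.

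| Record | SAP rule | Amended rule |
|---|---|---|
| A. Starts 10 January, mild; reassessed severe on 22 January; one record | No | Yes |
| B. Same worsening, entered as a new AE starting 22 January | Yes | Yes |
| C. Starts 18 January, mild | Yes | Yes |
| D. Starts 10 January, mild, never worsens | No | No |

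Only A changes. The amended rule does not bring in D. A and B are clinically the same event, so under the SAP rule the result depends on how the site entered it.

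**3. Trace record A through the planned output (SAP sections 3.7.1, 3.7.1.1 and 3.3.1).**

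- Excluded: any TEAE, overall and by maximum severity; TESAE; TEAE leading to discontinuation of study, of Remodulin or of Orenitram; the system organ class and preferred term tables for those categories; the listing of TEAEs leading to discontinuation of study drug.
- Still present: the any-SAE row and the row for SAEs leading to death, where they apply; the SAE listing; the by-subject listing of all AEs. If it is one of the seven prostanoid AEs, it can also appear in the by-phase summaries, and the symptom in the Bothersome Survey. Disposition counts still show that study drug was stopped.
- A non-serious, non-prostanoid AE that worsens appears, as an AE, only in the by-subject listing.

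**4. Size.** The documents give no frequency for AEs that start in the pre-dose window and later worsen, so no count can be computed. The effect of one misclassified subject is 100/n percentage points:

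- n = 35 (SAP section 2.2.3): 100/35 = 2.9 points
- n = 30 (Protocol section 10.2): 100/30 = 3.3 points
- n = 10 (interim, SAP section 4.1): 100/10 = 10 points

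The figures 35 and 30 are targets for evaluable subjects. The Safety Population is everyone dosed; if it is larger, the shift per subject is smaller. The shift arises only in rows where the subject has no other qualifying event.

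**The case against.** The best defence is that most of what a reader would worry about is shown elsewhere. A reader might infer that a mild screening headache that turns severe on Remodulin disappears from the safety report. The documents do not support that. Headache, nausea, diarrhea and extremity pain are all on the prostanoid list. Those AEs are summarised by treatment phase at that phase's maximum severity, with no stated restriction to TEAEs, and the Bothersome Survey reports change from Baseline for the same symptoms. This stands for the final analysis, with one reservation: the SAP's carry-over rule concerns AEs spanning more than one treatment phase and does not explicitly address onset before the first phase. It does not help the interim, where those tables are not listed.

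A second defence is that sites may enter worsening as a new AE, as Protocol section 9.1.1 could be read to allow. Such a record is captured (record B). So one cannot say that worsening is never entered separately, and the eCRF completion guidelines are not among the documents. But neither document instructs sites to open a new record, and the reassessment structure points the other way. The flag should not depend on that choice.

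Third, the affected group is narrow. The AE must begin after consent, within a window of up to 28 days, be ongoing at first dose, worsen, and stay in one record. Symptoms that predate consent belong to medical history, and their worsening can be a new AE. The study is also uncontrolled and descriptive. All of this stands and limits the size of the problem, but the stated rule still gives the wrong answer for the records it reaches.

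**Conclusion.** The point holds, with limited reach. Followed as written, SAP section 3.7.1 leaves a pre-dose AE that worsens on drug, and is kept as one record, out of every treatment-emergent row, table and listing. It does not remove such events from all safety output. The clearest gaps are non-serious, non-prostanoid AEs, the TESAE and TEAE-discontinuation summaries, and the interim AE overview.

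The size is probably small. One misclassified subject moves an affected row by about 2.9 points if about 35 are dosed, or about 10 points at the interim. A reader might want to put a number of lost subjects, or a corrected TEAE rate, on this; the documents give no basis for either. The conclusion assumes that at least some sites record worsening as a reassessment, which the SAP's structure implies but does not prove. The definition should be corrected before the SAP is finalised.

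**What to change.** Replace the definition in SAP section 3.7.1 with: a TEAE is an AE that starts on or after the first dose of Remodulin, or that starts before it and has a reassessment of higher severity after that dose. Name the comparator; the last severity recorded before the first dose would fit the SAP's own definition of Baseline.

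In the TEAE tables, take severity as the post-dose maximum. The current rule takes the maximum over the whole record, so an AE that was severe, eased to mild before dosing and became moderate on drug would be tabulated as severe.

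Also include pre-dose AEs that become serious after the first dose, where the date of becoming serious is available. The documents show reassessment dates with severity only, so this part needs a check of what the eCRF holds.

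The cost is a short SAP edit and a change to the flag's programming. The severity part needs no new data, because the SAP already relies on reassessment dates. TEAE rates may rise slightly. Moving from after to on or after the first dose may bring in Day 1 AEs that began before the dose, unless the onset times required by Protocol section 9.2 are used to separate them.

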2.2.3 Sample Size Determination

A sample size of approximately 35 evaluable subjects (i.e. completing the week 16 study visit without any major deviations which may interfere with study endpoints) was set for feasibility and to ensure a reasonable dataset to evaluate the Orenitram dose achieved, the clinical response to Orenitram after an induction period with Remodulin, and to assess the safety and tolerability of Orenitram after induction therapy with Remodulin. No formal sample size computation was performed with respect to the primary endpoint.

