4 ANALYSIS TIMING

4.1 Interim Analysis

An interim analysis will be performed when there are about 10 subjects that have conducted the Week 16/ Early Study Withdrawal Visit, to evaluate the safety of Orenitram after induction therapy with Remodulin. The safety profile will be used to check if it is consistent with the historical data on transitions gathered from previous studies.

The following summary tables and listings will be generated for the interim analysis based on the enrolled subjects who have conducted the Week 16/ Early Study Withdrawal Visit:

- Summary of disposition on enrolled subjects as described in section 3.3.1
- Summary of demographic and baseline characteristics will be provided as described in section 3.3.4
- Summary of REVEAL 2.0 risk score as described in section 3.3.5
- Summary of current PAH background medications as described in section 3.3.6
- Summary of study drug exposure (dosage and transition) will be provided as described in section 3.3.7
- The primary and key secondary endpoints (6MWD, Borg dyspnea score, WHO FC and NT-proBNP) will be summarized as described in section 3.4.1 and 3.4.2
- A listing of Remodulin and Orenitram dose levels for each subject at each timepoint will be provided by visit
- Overview summary of AEs as described in section 3.7.1

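### Apart from the prostanoid summaries and the drug-specific discontinuation rows, no planned AE or SAE summary separates events after the start of Orenitram from events on Remodulin alone

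*SAP*

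**What the plan says.** The safety question is about Orenitram. SAP 2.1.2 sets the secondary objective as the effect of Orenitram, after Remodulin induction, on clinical response, safety and tolerability. SAP 2.2.3 justifies the sample size partly by the wish to assess safety and "tolerability of Orenitram after induction therapy with Remodulin". SAP 4.1 gives the purpose of the interim as "to evaluate the safety of Orenitram after induction therapy with Remodulin", with the safety profile to be checked against historical data on transitions.

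The general AE tables start earlier. In SAP 3.7.1, TEAEs "are defined as AEs that start after the first dose of Remodulin". Collection starts earlier still: "Adverse events will be captured from when the subject signs the informed consent form (ICF) until the subject completes the study". The overview is described once ("An overview of AEs will be provided including counts and percentages of subjects and event counts") and lists any TEAE, any SAE, any treatment-emergent SAE, TEAEs leading to discontinuation of the study, of Remodulin and of Orenitram, and SAEs leading to death. Tables of the same categories, except any SAE, follow where there are at least five events: "Counts and percentages of subjects and event counts will also be presented by system organ class and preferred term". SAP 3.7 puts all of this on the Safety Population, which SAP 3.2.1 defines as subjects who received Remodulin or Orenitram.

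SAP 3.1.4 defines the three treatment phases. In SAP 3.7.1 the phase split is mandatory only for the seven prostanoid AEs. The only AE item listed for the interim is "Overview summary of AEs as described in section 3.7.1".

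**The concern.** The plan asks one question and, for general AEs, tabulates another. A subject with an SAE on Day 20 who transitions at the nominal Week 4 visit (Day 29) and has no later event is counted as having a treatment-emergent SAE. So is a subject with an SAE who stays on Remodulin throughout, which the footnotes to the SAP schedule table allow. Neither event arose on Orenitram, and nothing in the overview marks the difference.

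What is at stake is whether the report can state, from a prespecified table, how many subjects had a TEAE or SAE once Orenitram was started. The phase definitions needed for that already exist but are not applied to these tables. The interim has the least to fall back on. It has the pooled overview but not the prostanoid tables, the AE Bothersome Survey or the AE listings, and SAP Section 5 says its results are meant for presentation.

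**Working it through.** The plan states no figure to reproduce: SAP 2.2.3 makes no formal sample size computation and SAP 3.1.6 plans no testing. The check is mainly textual, with arithmetic for scale.

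**Step 1: which AE summaries isolate time on Orenitram?**

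| Planned output | Counted from | Separated by phase or drug? |
|---|---|---|
| Any TEAE, any treatment-emergent SAE, TEAEs leading to study discontinuation | First Remodulin dose | No |
| Any SAE, SAEs leading to death | Consent (in subjects later dosed, since the Safety Population requires study drug) | No |
| Organ class and preferred term tables | As the matching overview row | As the matching overview row |
| TEAEs leading to discontinuation of Remodulin, of Orenitram | First Remodulin dose | By drug, not by phase |
| Seven prostanoid AEs, with maximum severity | By phase | Yes |
| AE Bothersome Survey (same seven effects) | Baseline, Transition Visit, Week 16/Early Withdrawal | Yes, as change from the Transition Visit |
| AE days by phase (in the prostanoid list) | By phase | Optional |
| By-subject listings of AEs, SAEs and TEAEs leading to discontinuation | All recorded events | Not a summary |

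No row gives the percentage of subjects with any TEAE or any SAE after Orenitram began.

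**Step 2: how much of the counted time is Remodulin alone?** The Week 16 visit is nominally Day 113, so follow-up is 113 − 1 = 112 days. Transition at Week 2, 4 or 8 is nominally Day 15, 29 or 57. The Remodulin-only share is (transition day − 1)/112:

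- Week 2: 14/112 = 12.5%
- Week 4: 28/112 = 25%
- Week 8: 56/112 = 50%
- Never transitioned: 112/112 = 100%

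**Step 3: share of event onsets in that time.** The documents give no event rates. Assume the Remodulin-only rate is k times the later rate, and let r be the Remodulin-only days. The share is k·r/(k·r + 112 − r).

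| k (assumed) | Week 2 | Week 4 | Week 8 |
|---|---|---|---|
| 1 | 12.5% | 25% | 50% |
| 2 | 22.2% | 40% | 66.7% |
| 3 | 30% | 50% | 75% |

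**Step 4: direction of the effect on the pooled percentage.** Two invented cases:

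- Higher: 10% of subjects have an event on Remodulin alone and, independently, 10% have one later. The pooled figure is 1 − 0.9 × 0.9 = 19%, against 10% after transition.
- Lower: 6 of 30 Orenitram-exposed subjects have an SAE, all after starting it, and 5 subjects who never transition have none. The pooled figure is 6/35 = 17%, against 6/30 = 20%.

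Among subjects who do start Orenitram, the pooled TEAE percentage cannot be below the percentage with onset after transition. Once never-transitioned subjects join the denominator, that ordering is lost.

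**The case against.** The strongest reply is that the plan already covers the safety question that matters most here. SAP 2.3.2.1 makes the prostanoid scores from the AE Bothersome Survey the secondary safety endpoint and places general AE incidence among the other assessments. The tolerability argument in Protocol 1.3 and 1.4 largely concerns prostanoid effects, and these are split by phase. TEAEs leading to discontinuation of Orenitram have their own row, covering every AE term, and that row is in the interim overview too. With about 35 subjects, SAEs could be assigned to phases from the listings in the final report.

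Much of this stands. A reader might infer that Orenitram's safety is answered only by a mixture of phases, and Step 1 shows that this is too strong. What remains is general TEAEs and SAEs that are neither prostanoid nor a cause of stopping Orenitram. For these, a listing permits reconstruction but is not a prespecified summary, and the AE listings are not among the interim outputs.

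A reader might also infer that the pooled percentage overstates the Orenitram figure by a known factor. With an assumed constant hazard of 0.002 per day, pooled risk is 1 − exp(−112 × 0.002) = 20.1%. Over the 98, 84 or 56 days after a Week 2, 4 or 8 transition it is 17.8%, 15.5% or 10.6%, giving ratios of 1.13, 1.30 and 1.89. But the daily rate is identical before and after transition in that calculation, so the ratios reflect only unequal follow-up. The hazard is not in the documents, each ratio supposes that everyone transitions at the same visit, and Step 4 shows that the direction can reverse.

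Nor do the documents show that the interim comparison is unlike with unlike. SAP 4.1 does not give the AE windows, populations or follow-up of the historical data. All that can be said is that the pooled overview does not isolate the period in question.

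**Conclusion.** The point holds as a gap in the planned summaries. The general TEAE, treatment-emergent SAE, SAE and death counts and the related organ class tables pool all phases, so the overall incidence of TEAEs or SAEs after starting Orenitram is not tabulated. The interim is the clearest instance.

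The part of the size that rests on the documents alone is the Remodulin-only share of time in Step 2, which uses nominal visit days. The distribution of transition visits and the number who never transition are unknown in advance, so no single figure applies to the trial. The event shares in Step 3 and the cases in Step 4 are illustrations on assumed rates and counts. The study is descriptive, so no error rate or power is affected. This is an inexpensive improvement worth making, not a defect that invalidates the safety reporting.

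**What to change.** In SAP 3.7.1, and in the overview used for SAP 4.1:

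- Keep the overall column and add Remodulin, Transition and Orenitram columns, as defined in SAP 3.1.4, to the rows for TEAEs, treatment-emergent SAEs, deaths and TEAEs leading to study discontinuation, and to the organ class and preferred term tables. Apply the five-event threshold to the overall count, so that splitting does not suppress a table.
- Use the number of subjects who entered each phase as the denominator. This matters: if 3 to 5 of 35 subjects never started Orenitram (assumed), the Safety Population denominator would shrink an Orenitram-phase percentage to 32/35 = 0.91 or 30/35 = 0.86 of its value among those exposed.
- Show exposure time per phase, because phases differ in length and bare percentages would not be comparable.
- Assign new events by phase of onset, and state how this relates to the prostanoid rule, which counts an event in every phase where it is present.
- Add a category for events starting after study drug is stopped, since Protocol 3.6 asks such subjects to stay to Week 16. Say also where events go after a reversed transition, when the subject is again on Remodulin alone.
- Base statements on Orenitram safety, and the interim check against transition data, on the Transition and Orenitram columns.

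The cost is SAP wording and extra columns. Protocol 9.2 already requires AE onset dates, and SAP 3.3.7 already uses first-dose dates and transition duration. The drawback is small counts per column, most of all at an interim with about 10 subjects.
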